1.0 Study Summary

Study Title	Brain Network Modulation and Alcohol Use
Study Design	This study seeks to investigate brain network modulation in individuals with alcohol use disorder (AUD). Enrolled participants will undergo a real-time fMRI scan and may be asked to complete corresponding questionnaires which will be submitted to the IRB for approval prior to use.
Primary Objective	Directly test the ability to modulate neural activity as a function of AUD severity using real-time fMRI.
Secondary Objective(s)	N/A
Study Population	Individuals who drink alcohol
Sample Size	50 participants
Research Intervention(s)/ Investigational Agent(s)	Data collection will include MRI data, including a real-time modulation task in-scanner, and relevant questionnaires.
Study Duration for Individual Participants	Participants will participate in one rtfMRI session. Prior to their fMRI, they will complete a brief interview to generate cues for use during their scan. We will retain personally identifiable study data for a period of seven years after completion of the study. After the period of 7 years has passed, we will destroy any personally identifiable study data.
Acronyms and Definitions	AUD=Alcohol Use Disorder AUDIT= Alcohol Use Disorders Identification Test fMRI=Functional Magnetic Resonance Imaging rtfMRI=real-time fMRI DMN=Default Mode Network FBRI=Fralin Biomedical Research Institute VTC=Virginia Tech Carilion HNL=Human Neuroimaging Laboratory BAAD = Brief Assessment of Alcohol Demand DD = Delay Discounting

2.0 Objectives

2.1 Describe the purpose, specific aims, or objectives of this study:

This study directly tests the ability to modulate neural activity as a function of AUD severity using real-time fMRI.

2.2 State the hypotheses to be tested:

We hypothesize that individuals with lower AUD severity will have a significantly higher correlation (indicating better modulation ability) than individuals with higher AUD severity.

3.0 Background

3.1 *Summarize the relevant prior research on this topic and gaps in current knowledge within the field of study:*

rtfMRI Background:

Functional magnetic resonance imaging (fMRI) is a technique that noninvasively measures correlates of neural activity (Ogawa et al., 1992) and allows the identification of cerebral substrates associated with processes that shape human awareness and perception, such as visual, auditory, emotional, somatosensory. Unlike positron emission tomography (PET), fMRI does not require the injection of intravenous tracers or exposure of the subject to any ionizing radiation. Another advantage of fMRI is that multiple scans can be obtained in a single (or multiple) imaging session(s), which allows for acquisition of 1000 scans over a few minutes, while a PET study is limited to 16 scans over 2 hours (Friston et al., 1995; Buckner et al., 1996). Thus, fMRI allows us to capitalize on increased temporal resolution and repetition of conditions capabilities in an effort to study brain function.

Pattern analysis of fMRI is a multivariate, supervised learning approach that is complimentary to univariate analyses – the data acquisition and experimental methods are identical.

As described by Hansen (Hansen et al., 1999), learning problems are generally designated as either supervised or unsupervised. Supervised learning deals with learning from examples, aiming to capture the functional relationships between variables, whereas unsupervised learning captures statistical relationships from the dataset itself. Examples of unsupervised learning applied to fMRI include principal components analysis (Hansen et al., 1999), independent component analysis (McKeown et al., 1998), and clustering techniques (Baumgartner et al., 1998; Hansen et al., 1999; Ngan and Hu, 1999). For brain state analyses, we are interested in multivariate relationships between fMRI images and the corresponding behavior or sensory parameters. Such relationships are usually obtained through the process of supervised learning. Though the majority of fMRI studies use univariate statistical methods, the supervised learning we are focused on generally relies on multivariate approaches. Emphasizing the multivariate aspect of brain state predictive analyses, several reports refer to this as “multi-voxel pattern analysis (MVPA)” (Haxby et al., 2001; Polyn et al., 2005; Norman et al., 2006). Compared with univariate GLM analyses, there are still relatively few multivariate, supervised learning studies, with early neuroimaging (PET and fMRI) work in predictive modeling developed by Strother and Hansen (Lautrup et al., 1994, Hansen et al., 1999, Kjems et al., 2002,

Kustra and Strother, 2001, Mørch et al., 1997, Strother et al., 2002, Shaw et al., 2003, LaConte et al., 2003a) and recent explicit testing of distributed brain systems by Haxby et al. (Haxby et al., 2001) and Cox and Savoy (Cox and Savoy, 2003). Continued innovation in methodology and creative experimental designs have since burgeoned (Mitchell et al., 2004; LaConte et al., 2005c; LaConte et al., 2007; Davatzikos et al., 2005; Haynes and Rees, 2005; Pessoa and Padmala, 2005; Kamitani and Tong, 2005; Polyn et al., 2005) It should be noted that the viewpoint that multivariate approaches can lead to new insights and are complementary to univariate analysis has been long and widely echoed (Friston et al., 1995; McIntosh et al., 1996; Moeller and Habeck, 2006). Moreover it is recognized that every method (univariate or multivariate) emphasizes some aspect of the data and cannot capture everything (McIntosh et al., 1996; Moeller and Habeck, 2006; Lange et al., 1999; Strother et al. 2002). To increase our understanding of brain function with fMRI, we must understand the relationships between highly multivariate brain images and categorical quantities describing discrete stimulus or behavioral responses (Victor, 2005). Comparing both, univariate approaches have benefited from much more methodological scrutiny and are highly interpretable and are often more statistically powerful in revealing localized activation. Their primary drawbacks are that they are highly vulnerable to detection limitations imposed by multiple comparisons, and validation of spatial activity is difficult (LaConte et al., 2003a). Multivariate approaches capture distributed relationships and are more powerful at detecting whether a particular stimulus condition is reflected in the data. They have been reported to reveal more information than univariate analyses (Lin et al. 2003; Fletcher et al, 1996). For predictive methods, validation can be performed when the stimulus/behavior of interest can be measured. Though not a specific aim, our general methods section discusses that post processing of all data collected will include comparison of our multivariate brains state models with GLM-based univariate activation patterns. Spatio-temporal properties of BOLD provide feasibility and utility for real-time systems. Blood oxygenation level dependent functional magnetic resonance imaging (BOLD fMRI) relies on changes in cerebral blood flow to indirectly measure neuronal activity (Bandettini et al., 1992; Kwong et al., 1992; Ogawa et al., 1990a; Ogawa et al., 1990b; Turner et al., 1991). The biophysics relating the BOLD signal to the underlying gray matter's neuronal electrical activity has been avidly studied since the introduction of the method. During a task, BOLD signal changes take 6-12 s to reach maximum intensity, where it remains relatively constant for sustained long periods of activity, and 8-20 s to return to baseline values after the task is finished (Chen et al., 1998; Kollias et al., 2000; Noll, 2001). Ultimate limits in timing may be much better than this since early but weak signal changes have been reported to occur roughly 0.5-2 seconds after the onset of neuronal activity (Kollias et al., 2000; Noll, 2001; Yacoub and Hu, 1999). In addition, temporal characteristics vary with spatial region (Chen et al., 1998), and importantly, subjects are capable of modulating strength and spatial extent of local activations, demonstrated by fMRI biofeedback studies (deCharms et al., 2004; deCharms et al., 2005; Yoo and Jolesz, 2002). The field strength of the scanner is also an important factor for real-time feedback studies as field strengths of 3 T or higher have important implications for the BOLD response (Yoo and Jolesz, 2002), namely increased specificity and signal-to-noise ratio (SNR). Recently fMRI, itself, has been evaluated for suitability as a biofeedback signal (deCharms et al., 2004; deCharms et al., 2005; Posse et

al., 2003; Weiskopf et al., 2003; Yoo and Jolesz, 2002). In the investigation by (Yoo and Jolesz, 2002), subjects were trained to interpret activation maps for a simple motor task with the goal of increasing activity in a localized brain region, and the five subjects examined were successful at the task of manipulating the spatial extent of their BOLD response. This result was corroborated and expanded by Weiskopf (Weiskopf et al., 2003) who showed significant changes of local BOLD responses in the anterior cingulate cortex in a subject who was provided with an updated display of level of activity in this area; (Posse et al., 2003) who showed that real-time feedback of amygdala activation in a sad mood task led to increases in both left amygdala activation and self-rated sadness; and DeCharms (deCharms et al., 2004), who directly demonstrated the ability of subjects to learn to exert voluntary control over somatomotor cortex activation using a real-time setup. Recent work of deCharms (deCharms et al., 2005) represents a particularly compelling example of the utility of real-time fMRI for therapeutic applications. This study examined the impact of providing BOLD signal level changes in the rostral anterior cingulate cortex (rACC) as feedback to affect conscious perception of pain. deCharms showed that when subjects increased (decreased) activity in this region, there was a corresponding increase (decrease) in pain perception, for a given pain stimulus. Such training was effective enough to lead chronic pain patients to report decreases in ongoing pain, even after completion of the experiment. Our concept of real-time fMRI provides uniquely different capabilities, and possesses several distinct advantages over existing implementations. The predictive learning framework requires training data, analogous to the functional localizer requirements in the other implementations. Focusing on multivariate relationships in the data, though, brain reading constitutes a distinctly different approach to existing real-time studies, which use time series fluctuations in localized regions as a biofeedback signal (deCharms et al., 2004; deCharms et al., 2005; Posse et al., 2003; Weiskopf et al., 2003; Yoo et al., 2004). By explicitly using distributed brain state patterns, our scientific perspective is that of brain reading rather than that of localized activation. The first advantage of this is that prior assumptions about functional localization and individual performance strategies are not required – it learns these directly from the volunteer. This provides for ultimate flexibility across the spectrum of cognitive domains. The second advantage is that feedback can rely on a direct, intuitive translation of brain state, rather than a display based on increasing or decreasing local activity. A subtle but important methodological consideration from DeCharms (deCharms et al., 2005) was that subjects required cognitive strategy guidelines to be successful. No similar coaching is necessary with our brain state approach – across the cognitive domains subjects were able to intuitively and accurately control cursor movement (LaConte et al., 2007). These advantages are supported by our preliminary results where we demonstrate that i) human-machine training can be accomplished in minutes, ii) near perfect accuracy of brain state is attainable during sustained periods of activation, iii) feedback can respond to changes in brain state much earlier than the time-to-peak of the BOLD response, and iv) great flexibility exists in terms of cognitive domain/psychological task. The shift in emphasis from offline to online analysis and consistent vs. changing behavioral responses raises exciting new challenges. The benefit of real-time feedback derived from brain state models is that it provides the potential for completely new experimental designs. This proposal focuses on dealing with the implications of this to support such experimental flexibility. Although the real-time

system that we have implemented is based on pattern analysis techniques that have been used in numerous studies (LaConte et al., 2003a; Cox and Savoy, 2003; Mitchell et al., 2004; LaConte et al., 2005c; Davatzikos et al., 2005; Haynes and Rees, 2005; Pessoa and Padmala, 2005; Kamitani and Tong, 2005; Polyn et al., 2005), these reports have used post-processing analyses. For offline laboratory analyses, the limitations of the BOLD response are really not that limiting. For example, it is possible to drop transition scans or shift the timing to account for the BOLD delay (LaConte, 2003; LaConte, 2005c, Mitchel, 2004). While these corrections are possible in training runs, in feedback testing runs (where the stimulus is being actively controlled) the BOLD delay can lead to errors or sluggish feedback. An important question is “how fast is fast enough?” Our answer is that this depends on the experiment and the type of cognitive processes being modeled. Rather than developing fMRI techniques that circumvent hemodynamic limitations in the hopes of approaching neuronal time scales, this project proposes characterizations that will enable better experimental designs given the current capabilities and limitations of blood flow-based neuroimaging.

For data acquisition, we use adaptations of standard stimuli for passive sensory perception, memory, etc. (e.g. flashing checkerboard, audio metronome, tactile (touch) stimuli, list of paired associate words/pictures) and internally and sensory cued motor tasks (e.g. foot, hand, or limb movements such as finger opposition, hand clenching, and rapid button pressing). When the scanner is running in real-time mode, we will provide feedback to the volunteer about their internal state (e.g. success of encoding paired associates, attention level, mood, motor performance).

In order to improve the process of data acquisition, we will be developing software additions to the Siemens image reconstruction code to automate data transfer to analysis computers in our lab. These changes in software are isolated from (the code will not have any access to) HIPAA sensitive information. In addition we will not be modifying the sequence itself so the MRI data acquisition and Siemens safety safeguards will not be altered. To summarize, we will be making software changes to streamline our experiments, but safety and privacy risks will not change.

AUD and Default Mode Network (DMN) Background:

Alcohol use disorder (AUD) remains a leading cause of morbidity and mortality in the United States, and most people who attempt to quit drinking relapse within six months. Since treatment efficacy seems in part to be a function of alcohol use severity, existing treatments could benefit from better brain measures that explicitly characterize the severity of AUD. Unfortunately, most imaging studies compare individuals with AUD to healthy controls – or if they do assess severity, only do so in one cognitive domain and in one sample. This research is influenced by the observation that the DMN is altered in AUD and in addiction generally. Although the DMN is typically more prominent in resting-state fMRI, analysis of task-based fMRI has suggested a plausible functional role for DMN activity in addiction.

3.2 Describe any relevant preliminary data:

Preliminary data collected with our rtMRI apparatus show that healthy participants can control DMN activity bi-directionally. This positions us to examine whether AUD individuals can apply similar control and if this ability is influenced by the severity of their addiction.

3.3 Based on the existing literature, provide the scientific or scholarly rationale for and significance of your research and how will it add to existing knowledge:

Based on these observations, this study directly tests the ability to modulate neural activity as a function of AUD severity using real-time fMRI. The real-time system has been used to demonstrate that healthy participants can successfully learn to gain volitional control over their own DMN activity, and that this ability appears to be impaired in psychiatric conditions. Individuals who drink alcohol, including those with AUD, will be recruited and consented into a real-time study. There are two neuromodulation tasks, which they may complete one or both of. The "DMN" neuromodulation task has them attempt to "focus/wander". The "BAAD" neuromodulation task instructs participants to modulate their brain activity toward a craving for alcohol or orient it toward a future goal. If there is time, and the participant is interested, they will also be given the opportunity to complete the other task to which they weren't initially assigned. In both tasks, participants will see their neural activity and attempt to increase and decrease its level prompted by neurofeedback. We will assess whether this ability is a function of AUD severity by correlating the neural activity with the experimentally-controlled "increase" and "decrease" cues, and then comparing this ability to AUDIT score.

4.0 Study Endpoints

*4.1 Describe the primary and secondary **study** endpoints. See links below for discussion of study endpoints and how they may differ from study objectives. These are most common in clinical trials but are sometimes applicable to other types of biomedical research, as well as social, behavioral, or educational research. See link below for a discussion.*

https://docs.google.com/document/d/1Wocz7K7a0hCQJPO_khh5l1SQjhGDDGHzcOPRHR5Tw/edit?usp=sharing

N/A

*4.2 Describe any primary or secondary **safety** endpoints. These should be included for all studies that are greater than minimal risk. (Minimal risk:*

The probability and magnitude of harm or discomfort anticipated in the research that are not greater in and of themselves than those ordinarily encountered in daily life or during the performance of routine physical or psychological examinations or tests.):

N/A

5.0 Study Design and Statistical Analysis Plan

5.1 *Describe the basic study design/approach (e.g., qualitative study using five focus groups of first year students to describe assimilation into the university community; randomized controlled trial of a behavioral change intervention to increase dietary intake of whole grains; pre- post-test evaluation of new pedagogical techniques to improve adult literacy):*

50 participants who drink alcohol, including those with AUD, will be recruited and consented into a real-time study intended to assess the relationship between AUDIT score and neural modulation. There are two neuromodulation tasks, which they may complete one or both of. The "DMN" neuromodulation task has them attempt to "focus/wander". The "BAAD" neuromodulation task instructs participants to modulate their brain activity toward a craving for alcohol or orient it toward a future goal. If there is time, and the participant is interested, they will also be given the opportunity to complete the other task to which they weren't initially assigned.

5.2 *Describe corresponding data analysis plan/approach (e.g., content analysis of focus group transcripts; descriptive analysis followed by linear regression modeling; nonparametric analysis of pre- and post-test measures):*

GLM-based analysis will be performed using AFNI (Cox, 1996). We will perform slice timing correction, motion correction, and spatial smoothing (Gaussian kernel with full-width-at-half-maximum of $2.0 \times$ the voxel size). The stimulus paradigms will be convolved with an ideal hemodynamic response function, and linear regression analysis will be performed to obtain linear regression coefficients (beta-weights) and t-statistic maps. In addition, we will perform support vector machine analysis using the 3dsvm AFNI plugin software we have developed.

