At the beginning of this visit, investigators of the study will review safety issues related to MRI with the subject and answer any questions. The primary procedure is an MRI scan. The MRI scanner we will use has a magnetic field of approximately 3.0T. Scanners with a 3.0T field strength have been approved for clinical use by the FDA and are currently available for routine clinical applications.

Prior to entering the scanner participants will be asked to read through instructions for the task with the researcher. Once instructions have been read through, the subjects will lie still in the MR scanner for a total of no more than 90 minutes, and studies will not exceed 2 hours. During the first several minutes acquisition of the structural scans will take place (T1-, T2-, and/or DTI-weighted), which will be followed by acquisition of the functional / real-time images. There are two real-time tasks, which they may complete one or both of (depending on time constraints). The "DMN" neuromodulation task starts with a resting-state scan and then has them attempt to "focus/wander". The "BAAD" neuromodulation task instructs participants to modulate their brain activity toward a craving for alcohol or orient it toward a future goal. The BAAD task itself assesses alcohol demand indices using three questions that ask participants about their drinking habits at different price ranges. They will respond to in-scanner Delay Discounting (DD) prompts. During "BAAD" training and neuromodulation, participants will view their previously-generated individualized images of alcohol and positive, goal-oriented life events. Anatomical scans will be repeated if the staff has reason to be concerned about participant motion which effects image quality. While the subject is inside the scanner, an

investigator will be in constant visual observation of the subject and in between scans will use voice-communication via an intercom to assure the subject remains comfortable. The subject will also have a hand-held squeeze bulb to signal the investigators at any point in the experiment. In the scenario the subject wishes to be withdrawn, the investigator will take the subject out of the scanner immediately. The behavioral tasks that are being proposed do not involve any administration of drugs or placebos or other treatments.

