11.0 Study Timelines

11.1 Describe:

- *The duration of an individual subject’s participation in the study (for example, 1 hour, 2-4 weeks, 3-5 years).*
- *The amount of time expected to enroll all study subjects (weeks, months, years, etc.)*
- *The amount of time expected for the investigators to complete this study including primary data analyses.*

Participants will participate in one rtfMRI session. The participants will lie still in the MR scanner for a total of no more than 90 minutes, and MRI sessions will not exceed two hours. The brief cue generation interview, completed prior to the scanning appointment, is expected to take 20 minutes, and will not exceed one hour. We will retain personally identifiable study data for a period of seven years after completion of the study. After the period of 7 years has passed, we will destroy any personally identifiable study data. Recruitment and enrollment

is anticipated to last 18 months. From start to completion, including data analyses, this study is anticipated to last two years.

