14.0 Number of Subjects

14.1 Indicate the total number of subjects to be enrolled and how this number was determined (e.g., sample size calculation [show], number of available subjects in a finite pool, number of tests funding award would allow):

G*power (Faul et al., 2007) determined the necessary sample size for this experiment - given a medium expected correlation of 0.4, we would need 42 participants (alpha = 0.01, Power = 0.8). We therefore propose to collect data from 50 participants.

14.2 If this is a multi-site study, indicate the number of subjects to be enrolled at this site and the total to be enrolled from all sites:

N/A

14.3 If applicable, indicate the number of potential subjects you expect to screen for enrollment, and the number of subjects you will need to complete the research procedures:

N/A

14.4 If the study has more than one procedure, indicate the total number of subjects to undergo each procedure separately:

N/A

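### Section 14.1's 42 participants do not follow from r = 0.4, alpha 0.01 and 80% power (68 or 59 are needed), and the calculation is tied to neither of the two tasks

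*Combined protocol and SAP*

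**What the plan says.** Section 14.1 credits G*Power with this result: "given a medium expected correlation of 0.4, we would need 42 participants (alpha = 0.01, Power = 0.8". It continues: "We therefore propose to collect data from 50 participants". It does not say whether the test is one- or two-sided. The hypothesis in 2.2 is directional: lower AUD severity goes with better modulation.

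Section 5.1 describes a DMN task and a BAAD task: "There are two neuromodulation tasks, which they may complete one or both of". Sections 3.3 and 5.1 have each person initially assigned to one task. If time and interest allow, "they will also be given the opportunity to complete the other task". Section 8.2 repeats the point: "There are two real-time tasks, which they may complete one or both of (depending on time constraints". Section 11.1 limits the opportunity: "Participants will participate in one rtfMRI session", with at most 90 minutes in the scanner.

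The hypothesis test is described only in 3.3. Neural activity is correlated with the increase and decrease cues, "and then comparing this ability to AUDIT score". Section 5.2 covers image preprocessing, GLM and support vector machine analysis, and does not mention AUDIT. Section 4.1 (endpoints) is answered N/A. So is 14.4, whose prompt reads "If the study has more than one procedure, indicate the total number of subjects to undergo each procedure separately".

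**The concern.** The statement in 14.1 is the only justification given for 50 participants. If its inputs do not produce 42, the reader cannot tell what power the study has.

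The calculation also assumes one score per person and one correlation, but the design can yield a DMN score, a BAAD score or both. If the second task is taken up by only some people, a single-task analysis has fewer than 50 participants. The plan gives no number from which to judge the loss.

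Because the analysis is left open, a DMN-only, BAAD-only or pooled result could each be reported as the test of the hypothesis. A null result could not be read against a known power.

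**Working it through.** **Inputs from the plan.** r = 0.4, alpha = 0.01, power = 0.80, stated n = 42, planned n = 50 (all 14.1). The null correlation is taken as 0. Sidedness is not stated, so results are given as two-sided / one-sided.

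**Step 1: try to reproduce 42.** Fisher z approximation: n = ((z_alpha + z_power) / atanh(r))² + 3, with atanh(0.4) = 0.4236 and z_power = 0.8416.

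- Two-sided: ((2.5758 + 0.8416) / 0.4236)² + 3 = 68.1
- One-sided: ((2.3263 + 0.8416) / 0.4236)² + 3 = 58.9

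The exact bivariate-normal test of a correlation gives 68 / 59. The point-biserial model gives 65 / 56. The lowest figure from any of these at the stated inputs is 56, so 42 is not reproduced.

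**Step 2: which input might differ?** Exact test, 80% power:

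| Reading | n needed (two-sided / one-sided) |
|---|---|
| r = 0.4, alpha 0.01 (as stated) | 68 / 59 |
| r = 0.5, alpha 0.01 | 42 / 36 |
| r = 0.4, alpha 0.05 | 46 / 37 |

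The second row gives exactly 42 two-sided (n = 41 gives 79.8%). That suggests a slip in r, but nothing in the documents confirms it.

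**Step 3: power delivered.** Exact test, one score per person. The rows for 25 and 35 assume that number do a given task and that the task is analysed alone; the plan states no per-task number.

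| n | r = 0.4, alpha 0.01 | r = 0.5, alpha 0.01 | r = 0.4, alpha 0.05 |
|---|---|---|---|
| 50 | 63% / 73% | 89% / 93% | 84% / 90% |
| 42 | 53% / 63% | 81% / 87% | 76% / 85% |
| 35 | 43% / 54% | 71% / 79% | 68% / 79% |
| 25 | 28% / 37% | 51% / 61% | 53% / 65% |

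At n = 50 and alpha 0.01, the smallest correlation detectable with 80% power is 0.46 / 0.43. The smallest n in the Step 2 table is 36, so a task done by 35 or fewer stays below 80% under all three readings. If all 50 do a task, there is no per-task loss.

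**Step 4: does averaging two scores help?** If each task's score correlates 0.4 with AUDIT and the two scores correlate c with each other, their mean correlates 0.4 / √((1 + c)/2) with AUDIT. With c = 0.5 this is 0.4 / √0.75 = 0.46, about the detectable limit at n = 50. Simulated power with 50 people, of whom m do both tasks (alpha 0.01, 100,000 runs; m and c are assumptions):

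| m doing both | c | Power (two-sided / one-sided) |
|---|---|---|
| 50 | 0.5 | 81% / 87% |
| 50 | 0.7 | 73% / 81% |
| 35 | 0.3 | 80% / 87% |
| 25 | 0.4 | 74% / 81% |
| 25 | 0.6 | 70% / 78% |

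Pooling can reach 80% or miss it. The result depends on uptake and on c, and the plan gives neither.

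**The case against.** The strongest reply accepts the arithmetic and disputes the task point. Section 3.3 speaks of one ability across both tasks, and 5.1 gives a single aim for 50 participants: the relation between AUDIT score and neural modulation. On that reading there is one modulation score per person, which matches the single correlation in 14.1, and only the handling of people with two scores is missing. The protocol also calls the MRI scan its primary procedure, so N/A in 14.4 may simply mean that all 50 undergo it. The AUDIT comparison is thin but not absent, since 3.3 describes it. Finally, if r = 0.5 or alpha 0.05 was meant, 50 is enough for one correlation and the error is only a slip.

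Much of this is fair, but it does not remove the problem. A pooled reading is plausible, yet no section states it, and pooling still needs a rule for mixing people with one score and people with two. The wording of 14.4 can be read either way, but the number per task then appears nowhere else. The last point is conceded: whether 50 is adequate depends on which input is wrong, and only the sponsor can say. The per-task and pooled figures illustrate the range; they are not predictions.

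**Conclusion.** The concern holds. As written, 14.1 is wrong: r = 0.4, alpha 0.01 and 80% power require 68 (two-sided) or 59 (one-sided), and the planned 50 gives 63% or 73%. This part rests only on the plan's own numbers and the standard test of a single correlation.

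It does not follow that the study is too small. Under the two alternative readings checked, 50 gives 84% to 93% for one correlation.

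The second part also holds: the plan gives no number per task, no pooling rule and no rule for two scores. How much power that costs cannot be derived from the documents. It ranges from nothing, if all 50 do the analysed task, to a large loss if about half do. Correcting 14.1 alone would leave a power figure attached to no defined test.

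**What to change.** 1. In 14.1, confirm the intended r, alpha and sidedness, correct whichever figure is wrong, and restate the power at 50. If r = 0.4 and alpha 0.01 stand, that is 63% two-sided or 73% one-sided.
2. In 14.4, replace N/A with the planned number for each task and the power at that number.
3. In 5.2, name one primary AUDIT analysis. This can be a named task, or a pooled model with a task term that handles people with two scores (for example, a random participant effect). Report the remaining per-task results as estimates with confidence intervals.

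The cost is an amendment to the wording of 5.2, 14.1 and 14.4. An accurate plan needs no extra enrolment or scan time. If the sponsor keeps r = 0.4, alpha 0.01 and the 80% target with one score per person, 50 falls short of the 59 or 68 required. The sponsor would then have to accept the lower power openly or enrol more. The other price is less freedom to choose the analysis later.
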